•	To assess duration of CR	•	Duration of CR is defined as time from first occurrence of CR to relapse from CR, progression or death due to any cause whichever occurs first for participants treated with sabatolimab at 800 mg Q4W.		
•	To assess time to CR/mCR	•	Time to CR/mCR is defined as time from start of treatment to first occurrence of CR or mCR as per investigator assessment for participants treated with sabatolimab at 800 mg Q4W.		
•	To assess duration of CR/mCR	•	Duration of CR/mCR is defined as time from first occurrence of CR/mCR to relapse from CR, progression or death due to any cause whichever occurs first for participants treated with sabatolimab at 800 mg Q4W.		
•	To assess duration of response (responding participants defined as hematological improvement (HI) or better, per modified IWG-MDS	•	Duration of response for participants who achieved HI or better per modified IWG-MDS Cheson 2006 criteria) as per investigator assessment until relapse or death. Participants who did not relapse or die are censored to last adequate response assessment		

Objective(s)	Endpoint(s)		
Cheson 2006 criteria) as per investigator assessment.	for participants treated with sabatolimab at 800 mg Q4W.		
 To assess Progression-Free Survival (PFS) 	• Time from start of treatment to disease progression (including transformation to acute leukemia per WHO 2016 classification), relapse from CR or death due to any cause, whichever occurs first for participants treated with sabatolimab at 800 mg Q4W.		
 To assess Leukemia-Free Survival (LFS) 	 Time from start of treatment to transformation to acute leukemia [as defined as ≥ 20% blasts in bone marrow/ peripheral blood (per WHO 2016 classification) or diagnosis of extramedullary acute leukemia or death due to any cause, whichever occurs first] for participants treated with sabatolimab at 800 mg Q4W. 		
 To assess Event-free Survival (EFS) 	• Time from start of treatment to lack of reaching CR within the first 6 cycles, relapse from CR or death due to any cause, whichever occurs first for participants treated with sabatolimab at 800 mg Q4W.		
To assess Overall Survival (OS)	• Time from start of treatment to death due to any cause for participants treated with sabatolimab at 800 mg Q4W.		
• Expansion (Part 2)			
• To avaluate the changes from			

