9.1.1.2 Post-treatment follow-up

For participants who discontinue treatment for reasons other than disease progression, death, lost to follow-up, or withdrawal of consent; efficacy assessments, and other required assessments will continue to be performed as per the assessment schedule (see Table 8-1) until disease progression, death, lost to follow-up, or withdrawal of consent.

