9.1.4 Early study termination by the sponsor

The study can be terminated by Novartis at any time for any reason. This may include reasons related to the benefit/risk assessment of participating in the study, practical reasons (including

slow enrollment), or for regulatory or medical reasons. In taking the decision to terminate, Novartis will always consider the participant welfare and safety. Should early termination be necessary, participants must be seen as soon as possible to perform their End of Treatment Visit (EOT) and the assessments for EOT as described in Table 8-1 and will be treated as a prematurely withdrawn participant. The investigator may be informed of additional procedures to be followed in order to ensure that adequate consideration is given to the protection of the participant's interests. The investigator or sponsor depending on the local regulation will be responsible for informing IRBs/IECs of the early termination of the trial.

In the event that the study is terminated prematurely, e.g. based on recommendation of the steering committee (see also Section 10.2.2), participants still receiving study treatment and who, according to investigator assessment, continue to benefit from the treatment, will be offered to complete study treatment as per protocol or through an alternate setting (see Section 9.2).

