 - **Study treatment modification:** all CR will be taken into account regardless of any study treatment component interruption, dose adjustment or permanent discontinuation.
 - **Concomitant medications and supportive care:** A participant may receive blood transfusion as supportive care and prophylactic treatment as clinically indicated (e.g. antiemetics, antibiotics, antifungals). All CR will be taken into account regardless of any concomitant medication administration including prohibited medications.
 - New anti-cancer therapy/HSCT: CR achieved after initiation of a new anti-cancer therapy or HSCT will not be taken into account.
- Summary measures: The CR rate and the 95% confidence interval (CI).

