The duration of response will be derived for participants treated with sabatolimab at 800 mg Q4W who achieve HI or better (prior to any new antineoplastic therapy, including HSCT) as per investigator assessment and is defined from the first occurrence of CR, mCR, PR or HI until relapse, progression or death due to any reason.

Relapse, progression or death occurring after HSCT will be considered as an event for the duration of response. The date of the event will be the date of relapse, progression, or death whichever occurs first. If the participant did not relapse, progress or die, the duration of response will be censored at the last adequate response assessment. If the participant started a new antineoplastic therapy without prior documented relapse or progression, the duration of response is censored at the last adequate assessment prior to the start of that therapy and thus any subsequent relapse, progression, or death will not be considered as an event for duration of response.

Duration of response will be estimated using the Kaplan-Meier method. The median duration of response along with 95% confidence interval will be presented.

Time to CR/mCR

The time to CR/mCR will be derived for all participants treated with sabatolimab at 800 mg Q4W and is defined from start of treatment to first occurrence of CR/mCR (prior to any new antineoplastic therapy, including HSCT). For participants who reached CR /mCR after HSCT or a new antineoplastic therapy, the time to CR/mCR will be censored at the time of HSCT or initiation of new antineoplastic therapy.

For participants who did not reach CR/mCR, a). if they did not progress, die or progress to acute myeloid leukemia either, the time to CR/mCR will be censored at the last adequate response assessment; or b). if they progressed, died or the disease progressed to acute myeloid leukemia, the time to CR/mCR will be censored at the maximum follow-up (last participant last visit).

Time to CR/mCR will be estimated using the Kaplan-Meier method. The median time to CR/mCR along with 95% confidence interval will be presented.

Event-free survival (EFS)

Event-free survival (EFS) is defined from the date of start of treatment to:

- Lack of complete remission within the maximum of first 6 months or 6 cycles (including C7D1 assessment) of start of treatment
- Progression/Relapse
- Death from any cause

Whichever occurs first.

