Participants treated with sabatolimab at 800 mg Q4W who failed to achieve CR within 6 cycles of treatment will have their EFS event documented at start of treatment. If participant discontinued treatment due to any reason (including death) prior to 6 cycles and without CR will be considered as EFS event documented at start of treatment date.

Progression/Relapse, or death events after HSCT, and transfusion of blood products, will be taken into account. However, Progression/Relapse, or death, occurring after initiation of new antineoplastic therapy, will not be considered an event and EFS will be censored at the last adequate response assessment prior to the new antineoplastics therapy.

In case of two or more missing assessments prior to documented progression, relapse or death, EFS will be censored at the last adequate response assessment prior to the documentation of relapse or death.

EFS will be estimated using the Kaplan-Meier method. The median EFS along with 95% confidence interval will be presented.

Progression free survival (PFS)

PFS is defined as the time from start date of treatment to date of relapse, progression (including transformation to acute leukemia per WHO 2016 classification) or death due to any cause. If a participant is not known to have relapsed, progressed nor died, then PFS will be censored at the last adequate response assessment (on or before the cut-off date). Progression/relapse or death occurring after a). HSCT, b). interruptions or c). discontinuation of study treatment due to any reason will be taken into account. However, Progression/Relapse, death occurring after initiation of new antineoplastic therapy will not be considered an event and PFS will be censored at the last adequate response assessment.

In case of two or more missing assessments prior to documented progression, relapse or death, PFS will be censored at the last adequate response assessment prior to the documentation of progression, relapse or death.

PFS will be estimated using the Kaplan-Meier method. The median PFS along with 95% confidence interval will be presented.

Leukemia Free survival (LFS)

LFS is defined as the time from start of treatment to transformation to acute leukemia as per investigator assessment defined as the following:

- \geq 20% blasts in bone marrow/ peripheral blood (per WHO 2016 classification)
- Diagnosis of extramedullary acute leukemia
- Death due to any cause

whichever occurs first.

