2.6.1.3 Handling of missing values/censoring/discontinuations for PFS, LFS and EFS

For participants without PFS/EFS/LFS events, PFS/LFS/EFS are censored at the last adequate assessment (response assessment for PFS/EFS, bone marrow/hematology assessment for LFS).

This is the last response/bone marrow/hematology assessment conducted that is not considered as unknown.

An event occurring after two or more consecutive missing response assessments (not done or unknown) is censored in the analysis at the last adequate response assessment before the event date and reason for censoring then summarized as 'Event documented after two or more missing response assessments'.

An exact rule to determine whether there are two missing assessments is therefore needed. This rule will be based on the distance between the last adequate response assessment date and the event date. If the distance is larger than threshold D_2 then the analysis will assume that there are two missing assessments. This threshold D_2 is defined as two times the protocol specified interval between the response assessments plus the allowed window around the assessments. The protocol defines that response assessment has to be done at least at the time of bone marrow assessments that are to be done:

- Pre-dose on C3D1, then
- From C7D1, bone marrow assessments will be performed every 3 cycles (12 weeks) until C13D1 (C7D1, C10D1, C13D1), then
- Every 6 cycles (24 weeks) until C25D1 (C19D1 and C25D1) and thereafter every 12 cycles (48 week, visit: C37D1, C49D1 etc.) and as clinically indicated during the treatment period).
- At least every 12 months during follow-up for efficacy

As per the protocol, a window of +/-1 week from the planned visit date is allowed for BMA procedures. During the post-treatment and survival follow-up phases, a visit window of +/-2 weeks is allowed.

The censoring reason will be summarized as:

- 1. Ongoing without event
- 2. New anti-cancer therapy
- 3. Withdrew consent
- 4. Lost to follow-up
- 5. Event documented after two or more missing response assessments
- 6. Discontinuation due to participant/physician/guardian's decision

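### The EFS early-stop rule does not follow the EFS remission window: a CR recorded in the window after treatment stops, or a stop due only to sponsor closure or rollover, can be a failure at time zero

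*SAP*

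**What the plan says.** SAP 2.6.1.2 lists as its first EFS event "Lack of complete remission within the maximum of first 6 months or 6 cycles (including C7D1 assessment) of start of treatment". Participants without CR within 6 cycles "will have their EFS event documented at start of treatment". The next sentence covers early stops: "If participant discontinued treatment due to any reason (including death) prior to 6 cycles and without CR will be considered as EFS event", again dated at start of treatment. Protocol 12.5.1.2 has the same early-stop sentence. Its window is 6 cycles only, with no mention of 6 months or C7D1.

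The EFS endpoint in Protocol Table 2-1 does not name a treatment stop as an event: "Time from start of treatment to lack of reaching CR within the first 6 cycles, relapse from CR or death due to any cause".

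The primary estimand in SAP 2.5.1.2 says "all CR will be taken into account regardless of any study treatment component interruption, dose adjustment or permanent discontinuation". Its limit is the start of new anti-cancer therapy or HSCT. Protocol 9.1.1.2 keeps participants under observation after a stop for reasons other than progression, death, loss to follow-up or consent withdrawal: "efficacy assessments, and other required assessments will continue to be performed as per the assessment schedule".

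SAP 2.6.1.3 lists censoring reasons for PFS, LFS and EFS, including consent withdrawal, loss to follow-up and "Discontinuation due to participant/physician" (or guardian) decision. It has no category for sponsor termination or rollover.

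**The concern.** There are two problems, both in the early-stop sentence.

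First, the window and the early-stop rule answer different questions. The window asks whether CR was reached by a fixed time. The early-stop rule asks whether CR had been reached when treatment ended. The SAP lengthened the window but left the early-stop sentence as it stood in the protocol. One participant can then have a CR that counts in the CR rate, a positive duration of CR, and an EFS time of zero.

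Second, the rule covers every reason for stopping. Protocol 9.1.1 lists study termination by the sponsor as a mandatory stop, and Protocol 9.2 foresees transfer to a rollover study. Neither tells us anything about the regimen, yet either would be scored as immediate failure.

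At stake are the EFS listing and any EFS estimate. SAP 1.2 keeps EFS in the abbreviated report. SAP 2.6.1.2 always lists individual times with event or censoring type, while Kaplan-Meier output depends on the data available.

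**Working it through.** **The plan's own figures.** The documents give none for EFS. The CR design figures reproduce: the chance of at least 36 CR in 70 is 0.8005 at a true rate of 39/70 (stated 0.800) and 0.0195 at 27/70 (stated 0.020). This point does not touch them.

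**The window.** Six cycles are 6 × 28 = 168 days. Six months are 6 × 30.4375 = 182.6 days, using the month length in SAP Section 4. Without cycle delays, the SAP window therefore closes about 14.6 days after six full cycles.

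**A worked case.** A participant stops in cycle 3 without CR, and the end-of-treatment marrow or an unscheduled assessment in month 4 shows CR, with no new therapy.
- Primary estimand: responder, because CR after permanent discontinuation counts.
- EFS window: CR reached in time.
- EFS early-stop sentence: stopped before 6 cycles and without CR at the stop, so an event at start of treatment.

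The last two disagree unless the words on absence of CR are taken to refer to the whole window, which the SAP does not say.

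**Size.** Kaplan-Meier survival just after time zero is S(0+) = 1 − d/n, where d is the number of events dated at start of treatment. SAP 1.1 plans about 12 participants at 800 mg in cohort 2, and the expansion will not open, so n is about 12. Each reclassified participant moves S(0+) by 1/12 = 8.3 points. At the planned n of 70 it would have been 1/70 = 1.4 points. The counts below are assumptions; the documents give none.

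*In-window CR after a stop*, with 6 of 12 primary responders (50.0%):
- none scored as an EFS failure: S(0+) = 6/12 = 50.0%
- one: 5/12 = 41.7%
- two: 4/12 = 33.3%

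*Stops due solely to sponsor closure or rollover*, a of them among the 6 of 12 without CR:
- scored as events (the current rule): 6/12 = 50.0% for any a
- censored: (6 + a)/12 = 58.3%, 66.7% and 75.0% for a = 1, 2 and 3

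**The median.** Since non-CR is dated at start of treatment, S(0+) falls to 50% or below whenever half or fewer reach CR. With n = 12 and no administrative stops at all, the chance of that is 0.86, 0.61 or 0.45 for a true CR rate of 39%, 50% or 55.7%. At exactly 6 of 12, the median depends on the convention used for a curve resting on 50%.

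**The case against.** The early-stop rule is pre-specified and appears in both documents. Counting an early stop without CR as failure is a recognised composite, and it matches the CR rate, where such a participant stays in the denominator as a non-responder. This stands for toxicity, consent withdrawal and loss to follow-up. Censoring the last two could be informative in an open-label trial, because participants who are not responding may be more likely to leave.

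A reader might infer four stronger things that the documents do not support.
- That the rule contradicts the censoring list in SAP 2.6.1.3. That section censors only participants without an event. The list serves three endpoints, and its reasons can still apply to EFS after a CR.
- That the sponsor's decision has already created false failures. SAP Section 1 reports a halt to recruitment, not to treatment. Protocol 9.1.4 does say that on early termination a participant "will be treated as a prematurely withdrawn participant", but it also offers those still benefiting continued treatment. No affected participant is shown.
- That a zero median would expose the rule. Ordinary non-response can produce one.
- That EFS as a whole is biased downward. Under the written composite, most early stops without CR are failures by definition.

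In-window CR after a stop may also be rare. Protocol 8.3.1 requires response assessment in efficacy follow-up only at least every 12 months, so such a CR would be seen mainly at end of treatment or at an unscheduled visit. None of this resolves the conflict between window and early-stop sentence, or gives sponsor closure a place in the rules.

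**Conclusion.** The point holds in a limited form. On the literal text, a CR recorded inside the EFS window after treatment has stopped counts for the primary endpoint and is still an EFS failure at start of treatment. A stop due only to sponsor termination or rollover is scored the same way. The effect is 8.3 points of S(0+) per affected participant, assuming 12 participants at 800 mg. The number affected is unknown and may be zero. EFS is a secondary, descriptive endpoint; the CR rate and its interval do not change. Treating toxicity, consent withdrawal and loss to follow-up without CR as failure is a defensible choice and is not part of the criticism.

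**What to change.** In SAP 2.6.1.2, replace the early-stop sentence with a rule tied to the SAP's own window. The event at start of treatment applies when no CR is recorded within the window before new antineoplastic therapy or HSCT, whether or not study drug has stopped. Use the same window in the sentence on non-response, which now mentions only 6 cycles.

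Make one exception: participants without CR whose treatment ended before the window closed solely because of sponsor termination or rollover are censored at the last adequate response assessment. Add that reason to the list in SAP 2.6.1.3.

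Keep other early stops without CR as events in the main analysis. Censoring consent withdrawal and loss to follow-up can be a sensitivity analysis, with a note that it may be informative.

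Record the change in SAP Section 3, because it departs from Protocol 12.5.1.2. The cost is a few lines of text, a programming condition on CR date and recorded stop reason, and possibly a few more censored observations.

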2.5.3 Handling of missing values/censoring/discontinuations

2.5.3.1 Cohort 2 of Safety run-in (Part 1) and Expansion (Part 2)

For the determination of CR, only assessments after first dose of study treatment and prior to the start of any other anti-neoplastic therapy/HSCT as per investigator evaluation are considered. An adequate response assessment is considered any disease assessment indicating response status apart from "unknown" or "not done". Participants who discontinued trial prior to the first efficacy assessment (i.e. C3D1) will be reported with best response as 'Unknown'.

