The duration of CR will be derived for participants treated with sabatolimab at 800 mg Q4W who achieve CR per modified IWG-MDS Cheson 2006 (prior to any new antineoplastic therapy, including HSCT) as per investigator assessment and is defined from the first occurrence of CR until relapse, progression, or death due to any reason. Relapse, progression or death occurring after HSCT will be considered as event for the duration of CR. The date of the event will be the date of relapse, progression, or death whichever occurs first. If participant did not relapse nor progress/die, the duration of response will be censored at the last adequate response assessment. If the participant has started a new antineoplastic therapy without prior documented relapse or progression, the duration of CR is censored at the last adequate assessment prior to the start of that therapy, and thus any subsequent relapse/progression/death will not be considered as an event for duration of CR.

Duration of CR will be estimated using the Kaplan-Meier Method. The median duration of CR along with 95% Confidence interval will be presented.

Duration of CR/mCR

The duration of CR/mCR will be derived for participants treated with sabatolimab at 800 mg Q4W who achieve CR or mCR (prior to any new antineoplastic therapy, including HSCT) as per investigator assessment and is defined from the first occurrence of CR or mCR until relapse, progression or death due to any reason. Relapse, progression or death occurring after HSCT will be considered as event for the duration of CR/mCR, the date of the event will be the date of relapse, progression, or death whichever occurs first. If the participant did not relapse, progress or die, the duration of CR/mCR will be censored at the last adequate response assessment. If the participant started a new antineoplastic therapy, without prior documented relapse or

Novartis	For business use only	Page 28 of 46
Statistical Analysis Plan (SAP)		MBG453B12203

progression, the duration of CR/mCR is censored at the last adequate assessment prior to the start of that therapy and thus any subsequent relapse/progression/death will not be considered as an event for duration of CR/mCR.

Duration of CR/mCR will be estimated using the Kaplan-Meier Method. The median duration of CR/mCR along with 95% Confidence interval will be presented.

Duration of response

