If a participant is known to not have progressed to leukemia as defined by the criteria mentioned above, then LFS will be censored at the last bone marrow/peripheral blood assessments (on or before the cut-off date). Any of the three events (i.e. $\geq 20\%$ blasts in bone marrow/peripheral blood, diagnosis of extramedullary acute leukemia or death) occurring after HSCT, interruptions, or discontinuation of study treatment due to any reason will be taken into account. However, events occurring after initiation of new antineoplastic therapy will not be considered

an event and LFS will be censored at the last adequate assessment of bone marrow and/or peripheral blood, or diagnosis of extramedullary acute leukemia prior to initiation of new antineoplastic therapy.

In case of two or more missing assessments prior to documented progression to leukemia, LFS will be censored at the last adequate assessment (bone marrow and/or hematology assessment) prior to the documentation of progression to leukemia.

LFS will be estimated using the Kaplan-Meier method. The median LFS along with 95% confidence interval will be presented.

Overall Survival (OS)

OS is defined as the time from start date of treatment to date of death due to any cause. If a participant is not known to have died, then OS will be censored at the latest date the participant was known to be alive (on or before the cut-off date). All deaths will be taken into account whenever the death occurred, i.e. even after new anti-neoplastic therapy, HSCT, interruptions, or discontinuation of study treatment due to any reason.

The OS censoring reason will be summarized as 'Alive' or 'Lost to follow-up'. Participants not known to have died will have the censoring reason 'Lost to follow-up' if the reason for discontinuation from study is 'Lost to follow-up' or 'Withdrawal of consent'. Otherwise, participants will have the censoring reason 'Alive'.

OS will be estimated using the Kaplan-Meier method. The median OS along with 95% confidence interval will be presented.

Improvement of RBC/platelets transfusion independence

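### SAP PFS rule drops events after new antineoplastic therapy but does not require the censoring date to precede that therapy; SAP 2.6.1.3 leaves a narrower version of the same gap for LFS and EFS

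*SAP*

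**What the plan says.** **PFS (SAP 2.6.1.2).** Progression, relapse or death after new antineoplastic therapy "will not be considered an event and PFS will be censored at the last adequate response assessment". For participants with no event, the only limit on the censoring date is the data cut-off. Events after transplant do count: "Progression/relapse or death occurring after a). HSCT, b). interruptions or c). discontinuation of study treatment due to any reason will be taken into account". Protocol 12.5.1.2 has the same PFS rule with the same open date, so the SAP inherited it.

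**Sibling endpoints (SAP 2.6.1.2).** For events after new therapy, "EFS will be censored at the last adequate response assessment prior to the new antineoplastics therapy". The LFS rule ends with the same limit: "or diagnosis of extramedullary acute leukemia prior to initiation of new antineoplastic therapy". For CR duration, "the duration of CR is censored at the last adequate assessment prior to the start of that therapy". Duration of CR/mCR and duration of response follow that pattern.

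**General rule (SAP 2.6.1.3).** "For participants without PFS/EFS/LFS events, PFS/LFS/EFS are censored at the last adequate assessment". The next sentence defines the term: "This is the last response/bone marrow/hematology assessment conducted that is not considered as unknown". New anti-cancer therapy is one of six censoring reasons to be summarised, and no date rule goes with it.

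**Adequate assessment (SAP 2.5.3.1).** "An adequate response assessment is considered any disease assessment indicating response status apart from" unknown or not done. The restriction in that section to assessments before other anti-neoplastic therapy or HSCT applies to determining CR.

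**The concern.** A rule that ignores events after a given time should also stop counting follow-up at that time. If events after new therapy are dropped but the participant is censored at a later visit, that participant stays in the risk set while unable to have an event. The listed PFS time is then too long. If switching is unrelated to prognosis, the Kaplan-Meier curve is also too high.

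The gap would be harmless if assessments stopped at the switch, but they need not. Protocol 9.1.1.2 continues efficacy assessments after treatment until progression, death, loss to follow-up or withdrawal of consent; starting new therapy is not on that list. Protocol 8.3.1 and Table 8-1 put response in efficacy follow-up at least every 12 months, and whenever clinically indicated.

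**Working it through.** No figure in the plan is at issue, so the check is a comparison of texts followed by an illustration of size.

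**Step 1: which censoring date applies to a participant who switches without a prior event?**

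| Endpoint | Event after the switch | No event after the switch |
|---|---|---|
| PFS | last adequate assessment, no pre-therapy limit | last adequate assessment up to cut-off |
| EFS | last adequate assessment before therapy | 2.6.1.3: last adequate assessment |
| LFS | last adequate assessment before therapy | last marrow or blood assessment up to cut-off |
| Duration endpoints | last adequate assessment before therapy | last adequate assessment before therapy |

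PFS is open in both columns. EFS and LFS are open only in the second, because their limiting clause is attached to events that follow new therapy. For them the censoring date depends on whether a later event happens. The duration endpoints cover every switcher without prior relapse or progression and have no gap.

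The EFS gap is narrow. A participant without CR within the first 6 cycles, or who stops treatment earlier without CR, already has an EFS event at the start of treatment. Only participants who reached CR in time, switched, and had no later event are exposed.

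**Step 2: one case.** A participant switches at month 5, has a response assessment at month 17 and dies at month 20. The death is dropped. As written, PFS is censored at month 17. With a pre-therapy limit it is censored at about month 5.

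**Step 3: how often a listed PFS time would change.** The documents give no switching rate, PFS median or follow-up at database lock, so these are assumptions:

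- PFS is exponential with median 9 months: h = ln2/9 = 0.0770 per month, unchanged after switching.
- Switching is independent, with hazard s = 0.0193 or 0.0086. The share switching before an event by 36 months is s/(h+s) × (1 − exp(−36(h+s))) = 0.194 or 0.096, called 20% and 10% below.
- There is an end-of-treatment assessment at the switch, then response visits every 12 months, the protocol minimum.

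A listed time changes only if the participant is event-free 12 months after the switch and that visit falls before the cut-off at month F. For one participant

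p = exp(−12h) × s/(h+s) × (1 − exp(−(h+s)(F−12))), with exp(−12h) = 0.397.

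For a cohort of 12, the chance of at least one change is 1 − (1 − p)^12.

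| F (months) | p, 20% | at least one of 12 | p, 10% | at least one of 12 |
|---|---|---|---|---|
| 12 or less | 0 | 0% | 0 | 0% |
| 15 | 0.020 | 21% | 0.009 | 10% |
| 18 | 0.035 | 35% | 0.016 | 18% |
| 24 | 0.055 | 49% | 0.026 | 27% |
| 36 | 0.072 | 59% | 0.035 | 35% |

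Simulation of the same set-up agrees within its error (0/21/35/48/60% and 0/10/18/27/35%). An affected time moves by at least 12 months, on average 12 to 16. The Kaplan-Meier median of the 12 is unchanged in 91-96% of trials at 20% switching over 15 to 36 months, and in at least 98% at 10%.

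The table counts scheduled yearly visits only. An unscheduled visit after the switch, including one that documents progression, would add cases.

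**Step 4: large-sample direction.** With the same assumptions, 36 months' follow-up and yearly visits, the Kaplan-Meier median is 9.0 months with a pre-therapy limit. As written it is about 9.5 at 20% switching and 9.2 at 10%.

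**The case against.** The strongest reply is that the intent is plain. SAP 2.6.1.3 separates new anti-cancer therapy from ongoing without event as a censoring reason, and every sibling rule points to a date before the therapy. Protocol EFS also lacked the limit; the SAP added it there and apparently missed PFS. This stands as to intent. A reader might infer that the sponsor chose to censor after the switch, and the documents do not support that. But the PFS sentence, followed as written with the SAP's own definition of the last adequate assessment, still gives the wrong date.

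A reader might also infer a larger distortion from the 12-weekly follow-up row in Table 8-1. With response visits that often, the large-sample median at 20% switching would go from 9.0 to about 9.8, and 60-87% of trials of 12 would have a changed time at 9 to 36 months. That row is for hematology. It notes alignment with response assessments, but response itself is required only at least yearly in follow-up, and SAP 2.6.1.3 reserves hematology for LFS. More frequent response visits are possible but not scheduled, so this is a high-side case.

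The pool of affected participants is also limited. Progression before a switch is already a PFS event and ends efficacy follow-up, and HSCT does not act as a censoring switch here.

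Finally, upward bias in the Kaplan-Meier curve is not automatic. It assumes that switching is unrelated to prognosis. If sicker participants switch, censoring before the therapy is itself informative and can also bias upward. Without an end-of-treatment assessment the two rules miss a true 9.0 by similar amounts in opposite directions (8.8 and 9.3). These points limit the claim about bias; they do not justify a censoring date after the switch.

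**Conclusion.** The point holds as a wording error in a secondary endpoint, with low impact. The SAP PFS rule drops events after new antineoplastic therapy and leaves the censoring date free to fall after it. SAP 2.6.1.3 does not repair this, and it leaves event-free switchers open under LFS and, among those who reached CR in time, under EFS. It would be too strong to say that EFS and LFS share the full PFS defect.

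In this trial the consequence lies mainly in individual listed times. The expansion was not opened, cohort 2 was planned at about 12 participants, and SAP 2.6.1.2 makes Kaplan-Meier output depend on the available data while always listing times and censoring types. On the assumptions above there is no change with follow-up of 12 months or less. At 15 to 36 months at least one listed time changes in about 10-35% of trials (10% switching) or 21-60% (20% switching), and the median rarely moves. The switching rates, the 9-month median and the independence of switching from prognosis are assumptions, not document figures.

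**What to change.** Change the SAP only. In the PFS paragraph of 2.6.1.2, and in 2.6.1.3 for PFS, EFS and LFS, write: *Participants who start new antineoplastic therapy (other than HSCT) without a prior event are censored at the last adequate assessment before that therapy starts, whether or not an event follows.* The HSCT exception is needed because all three endpoints count events after transplant.

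A separate minor point can be settled in the same edit. In 2.6.1.1 and 2.6.1.2 the transfusion-independence rate counts weeks after the start of treatment, but each period's duration runs from the end of the last transfusion with no floor at first dose. Transfusions are recorded for 16 weeks before first dose (Protocol Table 8-1), so pre-treatment weeks can be credited. Start each post-baseline period at the later of the last transfusion end date and the first dose of study treatment.

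The cost is two or three sentences, with no protocol amendment and no new data. PFS times of affected switchers, EFS and LFS times of event-free switchers, and some transfusion-independence durations become slightly less favourable.
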